15.6.4 Secondary Objective #4: T_{Regs}

Objective	To assess whether percent T _{Reg} levels increase further after vaccine 1
Analysis Set	All treated patients
Outcome	Maximum peak increase from vaccine 1 in percent T _{Reg} of CD4+ T cells
Hypothesis	With no additional temozolomide treatment after vaccine 1, the level of percent T _{Reg} will not significantly increase above vaccine 1 levels. Rather there should be no change or a reduction in T _{Reg} levels.
Analysis Plan	A one-tailed t-test will be conducted to assess whether the mean for the maximum change from vaccine 1 in percent T _{Reg} is significantly greater than 0. If the mean change is less than 0.71 (i.e. near 0 or a decrease), we will infer that levels of percent T _{Reg} do not increase after vaccine 1. Rather, they are either stable or decrease.
Power Analyses	In ATTAC-GM, the mean change in the percent T _{Reg} of CD4+ T cells between leukapheresis and vaccine 1, a period during which DI-TMZ is administered, was 5.77 (SD=4.52). Between vaccine 1 and the next cycle of DI-TMZ, the peak mean increase in percent T _{Reg} from vaccine 1 was -1.104 (SD=1.65). Assuming 48 patients and SD=1.65 for the mean change from vaccine 1 within I-ATTAC, there will be 90% power to detect an increase from vaccine 1 in the percent of T _{Reg} if the true mean increase is 0.71 or greater assuming a one-tailed test ($\alpha=0.05$).
Additional Analyses	If the primary analysis that examines the maximum increase from vaccine 1 percent T _{Reg} of CD4+ T cells observed at any point after the initial vaccine detects such an increase, the timing of that increase is of interest. Hence, we will also examine the change from vaccine 1 to each of the follow-up assessments (leukapheresis 2, vaccine 4, vaccine 5, and vaccine 6). A generalized linear model may be used to explore these longitudinal changes. We may also use one-tailed t-tests to describe these changes. The change between vaccine 1 to leukapheresis 2 reflects the impact of vaccine 1, 2 and 3; whereas the change at vaccine 4 reflects the effect of the first 3 vaccines as well as T _d pre-conditioning.

	We will also conduct a t-test to examine the change in T _{Reg} levels observed before DI-TMZ and vaccine 1 to confirm that T _{Reg} levels are elevated with DI-TMZ, as well as the change between leukapheresis 1 and initiation of DI-TMZ.
--	---

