8 OBJECTIVES AND ENDPOINTS

Table 1. Objectives and Endpoints

	Objective	Endpoint	Analysis
Primary	Determine if Td preconditioning of pp65 loaded DC vaccination with GM-CSF extends overall survival.	Median survival from initiation of dose intensive adjuvant temozolamide.	See Section 15.5
Secondary	Assess the association between migration of CMV pp65 RNA-pulsed DCs with GM-CSF to site-draining inguinal lymph nodes after Td pre-conditioning and subsequent survival. (PLEASE NOTE: With Protocol v.20220204, this objective has been removed as it was already addressed in a previous study.)	For survival after vaccine 4, the hazard ratio associated with a 1 unit increase in migration, defined as the maximum percentage of ^{111}In -labeled DCs reaching inguinal nodes during the 48 hours after the 4 th vaccination.	See Section 15.6.1
Secondary	Assess the association between CCL3 measured post-Td pre-conditioning and subsequent survival.	For survival after vaccine 4, the hazard ratio associated with a 1-unit increase in CCL3 measured post-Td pre-conditioning at vaccine 4.	See Section 15.6.2
Secondary	Assess the association between fold changes in T cell polyfunctionality and subsequent survival.	Mean fold change from baseline in the frequency of pp65 antigen-specific CD8 ⁺ T cells producing three or more cytokines (IFN γ , CCL3, IL-2, TNF α , CD107a) at leukapheresis 2 $14 \pm (4)$ days after vaccine 3. Mean fold change from baseline in the frequency of pp65 antigen-specific CD8 ⁺ T cells producing three or more cytokines (IFN γ , CCL3, IL-2, TNF α , CD107a) at vaccine 6. For survival after vaccine 4, the hazard ratio associated with a 1-fold increase in the frequency of pp65 antigen-specific CD8 ⁺ T cells producing three or more cytokines (IFN γ , CCL3, IL-2, TNF α , CD107a).	See Section 15.6.3
Secondary	Assess whether T _{Reg} levels remain low without adjuvant temozolamide.	Maximum mean peak increase from vaccine 1 in percent T _{Reg} of CD4 ⁺ T cells.	See Section 15.6.4
Secondary	Assess the safety of DI-TMZ treatment followed by DC vaccination.	Proportion of patients who experience unacceptable toxicity.	See Section 15.6.5
Exploratory	Assess the association CCL3 levels and migration.	Mean fold change in CCL3 between pre- and post-Td pre-conditioning. Correlation between CCL3 change from fold change in CCL3, and migration.	See Section 15.7.1

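### The T-Reg test compares the mean of each patient's highest change with 0, but under stable T-Regs that mean lies above 0, so the nominal 5% test rejects too often

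*Combined protocol and SAP*

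**What the plan says.** Section 15.6.4 asks whether percent T-Reg rises further after vaccine 1 once no more temozolomide is given. The hypothesis is no change or a reduction.

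- **Test.** A one-tailed t-test asks "whether the mean for the maximum change from vaccine 1 in percent" T-Reg "is significantly greater than 0".
- **Second criterion.** A mean change below 0.71 will be read as stable or decreasing.
- **Scope of the maximum.** Additional Analyses describes it as the increase "observed at any point after the initial vaccine", and names leukapheresis 2 and vaccines 4, 5 and 6 as the follow-up assessments. The T-Reg time points in Section 12.7.5 include the same four.
- **Power.** 90% for a true mean increase of 0.71, with 48 patients, SD 1.65 and one-tailed alpha 0.05.
- **Source of the SD.** The ATTAC-GM pilot: "Between vaccine 1 and the next cycle of DI-TMZ, the peak mean increase" in percent T-Reg was -1.104 (SD 1.65).
- **Table 1 in Section 8.** The endpoint reads "Maximum mean peak increase from vaccine 1 in percent" T-Reg of CD4+ T cells.

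Nothing in the plan adjusts the null value, the 0.71 cut-off or the power figure for taking a maximum.

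**The concern.** A one-sample t-test against 0 is calibrated only if the tested quantity has mean 0 under no change. A single-visit change meets that condition, but the largest of several changes does not. It picks each patient's most upward fluctuation, so its mean is positive even if T-Regs are flat at every visit.

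Two consequences follow. First, the test leans towards declaring a rise in the situation the sponsor hopes to demonstrate. Second, the maximum depends on how many visits a patient attends. Vaccination stops at progression (Section 12.3), so the endpoint mixes T-Reg behaviour with time on vaccine.

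The pilot figures do not calibrate the null. They cover only the interval up to the next cycle of dose-intensified temozolomide. This trial has no such cycle and looks for the peak out to vaccine 6.

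**Working it through.** **Inputs from Section 15.6.4.** n = 48, SD = 1.65, one-tailed alpha = 0.05, target 0.71, null value 0, four later visits.

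**Assumptions.** The documents give neither a visit-to-visit correlation nor a single-visit SD. I apply 1.65 to each single-visit change and vary the correlation rho between changes from 0.5 to 0.95. A rho of 0.5 is what a shared, equally noisy baseline produces when all variation is visit noise. Real differences between patients in their change push rho higher.

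**1. The plan's own power.** Noncentrality = 0.71 / 1.65 × √48 = 2.98 on 47 df. Power is 90.2%, which matches the stated 90%. The figure therefore treats the tested quantity as an ordinary change centred on 0 under stability. With SD 1.65 the smallest significant mean is 1.678 × 1.65 / √48 = 0.40.

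**2. Mean of the maximum under zero true change.** Write each change as a shared patient component (variance rho × 1.65²) plus an independent visit component (variance (1 − rho) × 1.65²). The expected maximum of four standard normals is 1.029, so

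E[max] = 1.029 × 1.65 × √(1 − rho) = 1.698 × √(1 − rho).

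**3. Behaviour of the test.** Simulation with 48 patients, four visits and zero true change. Simulation error is a point or two.

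| rho | mean maximum | t-test rejects | mean above 0.71 |
|---|---|---|---|
| 0.5 | 1.698 × 0.707 = +1.20 | about 100% | 99% |
| 0.8 | 1.698 × 0.447 = +0.76 | 96% | 59% |
| 0.9 | 1.698 × 0.316 = +0.54 | 74% | 24% |
| 0.95 | 1.698 × 0.224 = +0.38 | 48% | 9% |

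A mean above 0.71 is in practice always significant here. The gap between the last two columns is therefore the share of trials in which the two criteria disagree: 96 − 59 = 37%, 74 − 24 = 50% and 48 − 9 = 39% at rho 0.8, 0.9 and 0.95.

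**4. Number of visits (rho 0.5, zero true change).** The mean maximum is 0, +0.66, +0.99 and +1.20 for one, two, three and four visits, and rejection is 5%, 91%, 99.9% and about 100%. If 40 patients have four visits and 8 have one (an assumed split), the mean is (40 × 1.20 + 8 × 0) / 48 = +1.00 and rejection is 99.9%.

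**5. True falls.** A constant fall shifts the mean maximum by the same amount.

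| true fall at every visit | rho | mean maximum | t-test rejects | mean above 0.71 |
|---|---|---|---|---|
| 0.5 | 0.5 | 1.20 − 0.50 = +0.70 | 96% | 48% |
| 0.5 | 0.8 | 0.76 − 0.50 = +0.26 | 30% | 2% |
| 1.104 | 0.5 | 1.20 − 1.104 = +0.10 | about 12% | about 0.1% |
| 1.104 | 0.8 | 0.76 − 1.104 = −0.34 | about 0% | 0% |

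**6. Per-patient average instead.** Its SD is 1.65 × √(rho + (1 − rho)/4), which is 1.30, 1.52, 1.59 and 1.62 at the four correlations. Its mean is 0 under stability and type I error is about 5%. Power for a true 0.71 rise is 98%, 94%, 92% and 91%.

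**The case against.** Five points can be made for the plan.

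- **The 0.71 rule.** The plan does not rely on the t-test alone, since a mean below 0.71 is to be read as stable. This stands in part. A reader might infer that stable T-Regs would almost always be reported as rising, or that a true fall of 0.5 would be called an increase in 96% of trials. The documents do not support either statement. The 96% is the t-test only, and the mean passes 0.71 in 48% of those trials at correlation 0.5 and 2% at 0.8. But the rule does not repair the test. It leaves the two criteria contradicting each other, and the plan does not say which prevails.
- **The size rests on unknown inputs.** This stands. Correlation 0.5 is near the unfavourable end, and 1.65 is attached to a pilot peak, not to a single visit. The direction is not in doubt: false rejection is still 48% at correlation 0.95.
- **The pilot peak was negative.** A real fall can offset the bias, and one of 1.104 largely does. The hypothesis also covers no change, however, and there the test fails. The pilot window was shorter and its number of visits is not given, so the figure does not show that the maximum is unbiased.
- **The wording is ambiguous.** Table 1 could mean the highest of the visit means. On that reading stable T-Regs give an expected value of +0.17, rejection of about 15%, and a mean above 0.71 in under 1% of trials (correlation 0.5). The Analysis Plan tests the mean of the maximum change, which points to one maximum per patient.
- **The stakes are limited.** This is the fourth of five secondary objectives, it lies outside the Bonferroni group in Section 15.6, and the bias runs against the sponsor's hypothesis. If an increase is declared, the visit-by-visit changes will be examined. That lowers the priority but does not make the test valid.

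**Conclusion.** The point holds for the test as written. With one maximum per patient over several visits, 0 is not the value expected under stable T-Regs, and the nominal 5% level is not kept. Under zero true change, false rejection runs from about 48% to about 100% over correlations 0.95 to 0.5. The 0.71 cut-off is passed in 9% to 99% of trials. These sizes assume SD 1.65 per single-visit change, 48 patients and four visits each.

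A reader might go further and conclude that the trial would usually report the opposite of the truth. That does not follow: it depends on a correlation the documents do not give, on which criterion governs, and on T-Regs being flat and not falling as they did in the pilot. The plan should be corrected, as a secondary-endpoint matter; the primary survival analysis is not affected.

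**What to change.** In Table 1 and Section 15.6.4, make the tested outcome each patient's average change in percent T-Reg from vaccine 1 over the available later assessments (leukapheresis 2 and vaccines 4, 5 and 6). Test its mean one-sided against 0 and keep the maximum as a descriptive summary.

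A mean post-vaccine-1 change from a pre-specified repeated-measures model is an alternative. It is a different estimate when patients leave vaccine early. It would also have to be written in, because the plan says only that a generalized linear model may be used to explore the longitudinal changes.

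Report the per-visit changes in Additional Analyses whatever the main result, and not only after a detected increase.

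The cost is wording in two places and no new samples. The drawback is that averaging dilutes a brief rise at one visit, which the per-visit changes would still show.

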15.6 Secondary Objectives

This study has five secondary objectives. The first 3 secondary objectives examine the impact of functional measures of CMV pp65-loaded DC vaccine efficacy on survival post-vaccine. These measures include migration (Section 15.6.1), fold change in CCL3 (Section 15.6.2), and fold change in pp65 antigen-specific polyfunctionality (Section 15.6.3). Power calculations will be provided for each of the secondary objectives. Power calculations for the three functional predictors of survival post-vaccine 4 will be adjusted to account for multiple comparisons using a Bonferroni correction, and will use a type I error rate of 0.0167.

The other secondary objectives include an assessment of whether the percent of T_{Reg} of CD4+ T cells remains stable or decreases without additional temozolomide after vaccine 1 (Section 15.6.4), and an assessment of the safety of the protocol's treatment regimen (Section 15.6.5).

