16.6 Protocol Amendments

All protocol amendments must be initiated by the Principal Investigator and approved by the IRB prior to implementation. IRB approval is not required for protocol changes that occur to protect the safety of a subject from an immediate hazard. However, the Principal Investigator must inform the IRB and all other applicable regulatory agencies of such action immediately.

Though not yet required, the CPC should be informed about any protocol amendments that potentially affect research design or data analysis (i.e., amendments affecting subject population, inclusion/exclusion criteria, agent administration, etc.).

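### Section 15.6.4 reuses 0.71, the true mean at which the T-Reg test has 90% power, as a cut-off on the mean change; at 48 patients and SD 1.65 it conflicts with the t-test for observed means from about 0.40 to just under 0.71

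*Combined protocol and SAP*

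**What the plan says.** The Analysis Plan row of Section 15.6.4 gives two rules in consecutive sentences.

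- The first is a significance test: "A one-tailed t-test will be conducted to assess whether the mean for the maximum change from vaccine 1 in percent" T-Reg exceeds zero.
- The second is a cut-off: "If the mean change is less than 0.71 (i.e. near 0 or a decrease), we will infer that levels of percent" T-Reg have not gone up after vaccine 1 and are either steady or lower.

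The Power Analyses row shows where 0.71 comes from. With 48 patients, SD 1.65 and one-tailed alpha 0.05, power is 90% "if the true mean increase is 0.71 or greater assuming a one-tailed test". The same row gives the pilot's peak mean change after vaccine 1 as -1.104 (SD 1.65).

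Four other places bear on how the rules should be read:

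- The Hypothesis row says the level "will not significantly increase above vaccine 1 levels".
- The Additional Analyses row turns to the timing of a rise if the analysis of the maximum increase "observed at any point after the initial vaccine detects such an increase".
- Section 15.6 describes the objective as assessing whether percent T-Reg "remains stable or decreases without additional temozolomide after vaccine 1".
- Table 1 (Section 8) words the endpoint as "Maximum mean peak increase from vaccine 1 in percent" T-Reg of CD4+ T cells.

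**The concern.** A power calculation has two different numbers in it. One is the true effect the test is likely to detect, here 0.71. The other is the observed value at which the test becomes significant, which is always smaller when power exceeds 50%. The plan takes the first and applies it as if it were a threshold on the result. A range of observed means then satisfies both rules, and they give opposite answers.

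The objective is meant to support a positive statement, that T-Regs stay level or fall once temozolomide stops. The cut-off is the only rule given for that statement, and no confidence bound stands behind it. A modest real rise could be reported as no rise even though the planned test had found it.

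A related difficulty concerns the endpoint. If it is each patient's largest change over several visits, its expected value lies above zero even when no visit mean changes. A test against zero then leans towards finding an increase.

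**Working it through.** **Inputs.** All are from Section 15.6.4 (n = 48, SD = 1.65, one-tailed alpha 0.05, alternative 0.71, pilot mean -1.104), except n = 40. That is the number expected to reach vaccine 4 in Section 15.6.2, used here as a sensitivity value.

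**1. Reproduce the plan's figure.** SE = 1.65 / √48 = 0.2382. The critical t on 47 degrees of freedom is 1.678. The noncentral t distribution at a true mean of 0.71 gives power 0.902, against the stated 90%. The true mean giving exactly 90% power is 0.707. So 0.71 is the power alternative.

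**2. Observed mean at which the test is significant.** 1.678 × 0.2382 = 0.3996, about 0.40. With n = 40, SE = 0.2609, critical t = 1.685 and the boundary is 0.44.

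**3. The overlap.** At n = 48 and SD 1.65 both rules apply for observed means from 0.40 to just under 0.71. Example: a mean of 0.70 gives t = 0.70 / 0.2382 = 2.94 and one-sided p = 0.0025, yet the second rule infers no increase. The overlap at n = 48 disappears only if the observed SD reaches 0.71 × √48 / 1.678 = 2.93.

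**4. How often it matters.** Normal data, n = 48, true SD 1.65. The conflict column allows for the SD being estimated in each trial.

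| True mean change | Rules conflict (significant and mean < 0.71) | Cut-off infers no increase |
|---|---|---|
| -1.104 (pilot) | about 0% | about 100% |
| 0 | 4.9% | 99.9% |
| 0.5 | 47.5% | 81% |
| 0.71 | 40% | 50% |

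At a true 0.71 the t-test fails to reject in 1 - 0.902 = 0.098, about 10% of trials.

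**5. What a supported claim would need.** If 0.71 were kept as a margin, a one-sided 95% upper bound below it requires an observed mean under 0.71 - 0.3996 = 0.31 at n = 48 and SD 1.65. With n = 40 the figure is 0.71 - 0.4396 = 0.27.

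**The case against.** The strongest reply is that the t-test plainly governs. It is stated first, the Hypothesis row is framed by significance, and the Additional Analyses row depends on the test detecting an increase. Much of this stands. A reader might infer that the sponsor could report whichever conclusion it preferred after seeing the data. The documents do not support that, because these rows lean towards the t-test. What remains is that no passage states precedence, and the cut-off is still the only rule offered for concluding stability or a fall.

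A second reply is that 0.71 is an informal limit for a negligible change. The plan glosses smaller values as close to zero, and 0.71 is about 12% of the 5.77-point rise reported between leukapheresis and vaccine 1 (0.71 / 5.77). But no passage justifies 0.71 as a margin, and the stated inference is that levels have not increased, not that any increase is small. The mean change in that sentence also cannot be the true mean, since a decision rule cannot use an unknown quantity.

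Third, the pilot change was -1.104, and there the conflict practically vanishes. That is correct and limits the practical weight. The 40% to 48% conflict rates need true rises of 0.5 to 0.71, which no passage predicts, although 0.71 is the size the section is powered to detect. The 50% figure also follows for any cut-off placed at the true mean; the fault is placing it there.

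On the endpoint, a reader might want a size for the upward bias of a per-patient maximum. The documents give no between-visit correlations, so none can be computed. Table 1's wording also permits the largest visit mean.

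**Conclusion.** The point holds. The value 0.71 is a power alternative used as a decision threshold, and it contradicts the test in the sentence before it. The range of 0.40 to just under 0.71 is conditional on n = 48 and an observed SD of 1.65. It starts at 0.44 with 40 patients and moves with the SD actually seen. Within it, a significant increase is labelled stable or decreased. At a true increase of 0.71 the cut-off misses the rise in half of trials, against about one in ten for the t-test; if T-Regs fall as in the pilot, the defect has almost no effect.

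The calculations treat the mean as that of 48 roughly normal changes. This concerns one secondary objective. A reader should not infer a threat to the survival analysis, the sample size, the futility look or the toxicity rules, because no passage links them to it. The change should be made, but it is not critical.

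**What to change.** 1. Delete the sentence that applies 0.71 to the mean change.
2. Name one endpoint in advance, as the mean change from vaccine 1 at a stated visit. Leukapheresis 2 and vaccines 4, 5 and 6 are already listed. Align Table 1 with it.
3. Let the one-tailed t-test on that endpoint alone decide whether an increase is detected. Do not read a non-significant result as stability.
4. Claim *no relevant increase* only if the one-sided 95% upper confidence bound is below a pre-specified, justified margin.
5. If both criteria are met, report *increase detected, smaller than the margin*. If neither is met, report *inconclusive*.
6. If the per-patient maximum is kept, report it descriptively and do not test it against zero.

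Operating characteristics for a single-visit mean, taking 0.71 as the margin for illustration, n = 48, and assuming SD 1.65 carries over to one visit:

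| True mean | No relevant increase | Both criteria met | Increase | Inconclusive |
|---|---|---|---|---|
| 0 | 89.9% | 0.3% | 4.7% | 5.1% |
| 0.5 | 21.1% | 0.8% | 65.6% | 12.5% |
| 0.71 | 4.7% | 0.3% | 89.9% | 5.1% |

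The price is that absence of an increase becomes harder to claim. At zero true change the upper bound passes in 90% of trials (89.9% + 0.3%), against 99.9% under the present cut-off. With 40 patients it passes in about 85%; by symmetry this equals the t-test's power of 0.848 at a true 0.71. At -1.104 it passes in about 100% at n = 48.

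No new patients or samples are needed. It is a wording amendment, and Section 16.6 applies: "All protocol amendments must be initiated by the Principal Investigator and approved by the IRB prior to implementation".

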15.6.5 Secondary Objective #5: Toxicity

Objective	Assess the safety of DI-TMZ treatment followed by DC vaccination.																		
Analysis Set	All patients who initiate DI-TMZ treatment.																		
Outcome	Proportion of patients with unacceptable toxicity as defined in Section 9.1.1.																		
Hypothesis	The toxicity profile associated with DI-TMZ followed by DC vaccination is safe.																		
Monitoring Plan	
Table A: Toxicity Monitoring Rules
 
  
 Number of patients accrued	Number of patients with unacceptable toxicity requiring accrual suspension	
   
 ≤ 5	≥ 2	
 
 6-11	≥ 3	
 
 12-17	≥ 4	
 
 18-23	≥ 5	
 
 24-29	≥ 6	
 
 30-34	≥ 7	
 
 35-39	≥ 8	
 
 ≥ 40	≥ 9	
  
 
Given that both long- and short-term toxicities are of interest in this study, it is not feasible to suspend accrual while toxicity is assessed as is often done in phase I trials. If the criteria in Table A are satisfied or there are other reasons for concern about the safety of patient treatment (e.g., treatment-related toxic death), accrual will be suspended and data will be carefully reviewed to determine if accrual should be permanently terminated or the protocol modified. Table A provides conditions under which accrual will be temporarily suspended and data carefully reviewed to determine the appropriate action, including permanent study termination, continuation with patient accrual after appropriate amendment, or continuation with patient accrual with no modification of the protocol. These guidelines have not been adjusted for differential length of follow-up of accrued patients.
 
If a death occurs within 30 days of DC vaccine administration, that is not attributable to progressive disease or other obvious non-study related cause (i.e. motor vehicle accident), enrollment of new subjects and all vaccinations will be suspended until review by the PI and IND sponsor has been completed and the FDA notified. If attribution of death is determined by the PI, IND sponsor or FDA to be possibly, probably, or definitely related to trial drug, then continued treatment of all enrolled subjects with trial drug will be suspended until the review is completed and recommendations for the study continuation have been
	Number of patients accrued	Number of patients with unacceptable toxicity requiring accrual suspension	≤ 5	≥ 2	6-11	≥ 3	12-17	≥ 4	18-23	≥ 5	24-29	≥ 6	30-34	≥ 7	35-39	≥ 8	≥ 40	≥ 9
Number of patients accrued	Number of patients with unacceptable toxicity requiring accrual suspension																		
≤ 5	≥ 2																		
6-11	≥ 3																		
12-17	≥ 4																		
18-23	≥ 5																		
24-29	≥ 6																		
30-34	≥ 7																		
35-39	≥ 8																		
≥ 40	≥ 9																		

	
issued and approved by FDA. Any death attributed to trial drug, regardless of the timeline with respect to last treatment, will result in suspension of enrollment and suspension of continued treatment for enrolled subjects until review by FDA is complete and recommendations for study continuation issued and approved.

TABLE B: Probability of Accrual Suspension	
Underlying unacceptable toxicity Rate	Probability of accrual suspension
0.05	0.036
0.10	0.200
0.15	0.502
0.20	0.784
0.25	0.936
0.30	0.987

	The probability of accrual suspension as a function of the true unacceptable toxicity rate is provided in Table B. These statistics were generated assuming toxicity outcome was known at the time of accrual, and ignored issues such as time to toxicity, accrual rate, and length of follow-up. Every 6 months from the time the first patient received vaccine #1, the toxicity experienced by patients accrued to this study will be summarized and reviewed regardless of the number of patients accrued to determine whether the overall toxicity profile of treatment is unacceptable or not.
Analysis Plan	The proportion of patients who experience an unacceptable toxicity as defined in Section [9.1.1](#)
Additional Analyses	Adverse events will be summarized in several other forms to satisfy scientific and monitoring needs, as well as various regulatory reporting needs (e.g. FDA, DCI Safety Oversight Committee, and ClinicalTrials.gov). For these summaries, the frequency of adverse events will be tabulated by the maximum grade experienced.

